#### 5.6. Adherence and resuming the treatment in patients assigned to the group treated with vaginal progesterone capsules.

Use of capsules at least during 80% of the exposure time, and resuming the treatment not later than 72 hours after discontinuation for any cause will be considered an acceptable adherence to treatment. If adherence of a patient is below 80% or the treatment is interrupted for more than 72 hours, she will be withdrawn from the study but considered in the final statistical analysis.

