#### 5.7. Study participant withdrawal

The progesterone cerclage pessary will be removed if the patient requests so, or if there is any adverse event not responding to treatment alternatives such as pathological vaginal discharge non-responsive to antibiotic therapy. These participants will not be replaced and the information collected from them will be included in the analysis since this is based on the intention-to-treat principle.

Follow-up of subjects withdrawn from the investigational product will be the same as the standard follow-up.

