### 9.1. Sample Size

The calculation of the sample size is based on the power to detect differences in the proportion of spontaneous delivery before 32 and 34 weeks of gestation between the cerclage pessary formulations with respect to the control group (vaginal capsules containing 200 mg progesterone). Collecting data from at least 90 women in each group will provide a power of at least 80% to detect differences at a rate of 40% or more using a two-tailed test with  $\alpha=0.05$  for a non-corrected Chi square.

We estimate that up to 10% of enrolled women may not complete the study, so it is planned to enroll at least 99 pregnant women per group to reach at least 198 treated with the cerclage pessaries, and 99 treated with soft progesterone capsules as control group (i.e., 99 per vaginal formulation).

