5. ANALYSIS CONVENTIONS

The statistical analysis will be made by ILS Clinical Research under the authorization of Laboratorio Andromaco S.A.

GENERAL PRINCIPLES

The statistical analysis will be provided to give a general summary of the study subjects and a vision of the efficacy and safety of the results. The data provided by the sites will be summarized for this purpose. Tables of absolute and relative frequencies will be constructed for the quality variables. All the percentages will be presented with a decimal. The quantitative variables will be summarized with the number of subjects participating (n), mean, standard deviation (SD), and median, maximal and minimal.

Two tailed test will be carried out for all the analysis and the type I error is 0.05 for continuous variables and the discrete variables. All p values shall be rounded to three decimal and the values under 0.001 will be presented as <0.001 and values greater than 0.999 will be presented as 1.000. A comparison of the treatment groups will be done with respect to the demographic and baseline characteristics using inferential statistical techniques to detect if any of these variables may condition the results in the dependent variables. Comparisons in qualitative variables will be carried out using the Cochran-Mantel-Haenszel (CMH) test of general association, while the comparisons in quantitative variables will be made with a test of comparison of means (ANOVA analysis of variance) for independent samples with normal distribution. In the cases of no normality on the continuous variables, or in case of not belonging to the exponential family for discrete data, the parametric tests will be replaced for nonparametric tests such as Kruskal-Wallis or Friedman. These tests will be presented in each table as deemed necessary. All confidence intervals will be two-tailed and at 95%.

Table 1: Study Schedule of Assessments

Activities	Visit 1	Visit 2	Visit 3	Visit 4	Visit 5	Visit 6	Visit 7	Final Visit
Demography	X							
Medical History	X							
Physical Exam	X	X	X	X	X	X	X	X
Gynecological Exam	X							
Vital Signs	X	X ¹	X ¹	X ¹	X ¹	X ¹	X ¹	X ¹
Transvaginal Ultrasound	X	X ²	X	X	X	X	X	X
Pre-birth Control	X							
Obstetric Background	X							
Lab Tests (Blood and Urine)	X							
Eligibility	X							
Vaginal Discharge	X	X ³	X ³	X ³	X ³	X ³	X ³	X ³
Randomization	X							
Pessary Insertion	X							
Acceptability and tolerance to the insertion	X							X
Concomitant Medications	X	X	X	X	X	X	X	X

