6. POPULATION DEFINITIONS

In order to meet the needs of the sub-groups of the Protocol, the following population sub-groups are defined:

Per Protocol (PP): It is defined as the subset of participants who meet the criteria of selection, who expressed their desire to participate in the study, who signed the informed consent form, that the drug has been administered to them and have completed all the visits required or till the termination of the pregnancy as per Protocol.

Intention to treat (ITT): It is defined as the subset of participants who meet the selection criteria, showing their desire to participate in the study, who signed the informed consent form, that the drug has been administered to them, who have at least completed the initial visit and at least one of the subsequent visits to the pessary referred to in the Protocol.

The main efficacy analysis will be carried out with a focus Per Protocol (PP), however it will also be carried out per Intention to Treat (ITT) all the analysis. Otherwise, the main safety analysis will be completed as ITT.

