10. EFFICACY ANALYSIS

STATISTICAL HYPOTHESIS

Null Hypothesis:

There is no difference between the methods of cerclage pessaries with a sustained release of 6.3 and 7.7 g of progesterone (Treatments B and C, respectively) with respect to the control method (Treatment A) for at least 20 weeks.

Alternative Hypothesis:

There is a difference between the Control Method (Treatment A) with respect to the one of cerclage pessaries with a sustained release of 6.3 and 7.3 of progesterone for a period of 4 to 5 months.

“There is a difference between the methods of cerclage pessaries with a sustained release of 6.3 and 7.3 g of progesterone (Treatments B and C respectively) with respect to the Control Method (Treatment A) for a period of 4 to 5 months”.

PRIMARY ANALYSIS

The primary objective is to evaluate the efficacy of two cerclage pessaries with doses of 6.3 and 7.7 g of sustained release micronized progesterone with respect to the standard treatment of 200 mg of progesterone in capsules administered daily. The primary efficacy analysis will be assessed by comparing the proportions of spontaneous premature delivery after 32 weeks but before 34 weeks of gestation, as primary results, among treatments through the CMH test. Also, the odds ratio and 95% confidence interval will be estimated, considering Group A as the control to be compared with groups B and C. Secondly, the comparison of proportions between the groups C and A will be done with the intention to confirm the significant difference between the highest dose and the standard treatment. Afterwards, the same comparison of proportions will be done with treatment B in order to establish the difference between the group of a minor dose and the standard. Finally the comparison between treatment B and C will be done hoping to demonstrate there is a difference of superiority between B and C where C must be minor than B regarding the number of low-risk pregnancies. The transitivity between treatments will be established according to the results. This is expected to be as follows:

$$\textit{Treatment C} < \textit{Treatment B} < \textit{Treatment A}$$

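### Women who leave the study can have an unrecorded delivery, by routes that differ between arms, and no rule says how such births enter the ITT and Kaplan-Meier analyses

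*Protocol*

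**What the plan says.** The Protocol wants withdrawn women analysed.

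- Section 5.5: a woman whose expelled pessary is not put back within 72 hours leaves the study but stays in the final analysis under intention to treat.
- Section 5.6: for capsule use below 80%, or a gap of more than 72 hours, "she will be withdrawn from the study but considered in the final statistical analysis".
- Section 5.7: for pessary removal on request or for an unresolved adverse event, "the information collected from them will be included in the analysis since this is based on the intention-to-treat principle". Women withdrawn from the product keep standard follow-up.
- Section 5.8: the pregnancy outcome comes from hospital records or the treating physician.
- Section 9.1: "We estimate that up to 10% of enrolled women may not complete the study". Enrolment is raised from 90 to 99 per group.

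The SAP is organised differently.

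- Section 6: the main efficacy analysis is Per Protocol, limited to women who completed the required visits or were followed to the end of pregnancy. Every analysis is repeated on an ITT set of women "who have at least completed the initial visit and at least one of the subsequent visits".
- Section 9: removal of the pessary means early termination from the study.
- Table 1: the Birth row is marked only at the Final Visit.
- Section 10: proportions are compared "among treatments through the CMH test". The Kaplan-Meier analysis censors elective deliveries; loss to follow-up is not mentioned there or in Protocol 9.

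Neither document has an imputation rule, a denominator rule or a sensitivity analysis for an unknown delivery.

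**The concern.** The endpoint needs a gestational age and a cause of delivery, or proof that the woman was still undelivered at the cut-off. A woman can join the SAP's ITT set at her second visit and leave the study before any of that is known. Her outcome can then be handled in three ways: counted as a non-event, dropped, or censored. These can give different answers, and in an open-label trial the choice should be fixed before the data are seen.

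The exits also differ by arm. Capsule users leave on a pill count or a treatment gap. Pessary users leave on expulsion, on request or for an adverse event. Unequal loss is therefore plausible. If unknown births were scored as non-events, the arm with more exits would look better than it is, and a poorly tolerated pessary could gain from its own withdrawals.

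**Working it through.** **1. The plan's dropout figure.** 90 × 1.10 = 99 per group (Protocol 9.1), so 9 of 99 are allowed as non-completers. Dividing instead, 90/0.90 = 100, which is close. This is non-completion and so only a guide to unknown births.

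**2. Other inputs.** "Two tailed test will be carried out for all the analysis" and "the type I error is 0.05 for continuous variables and the discrete variables" (SAP 5). Protocol 9.1 names the uncorrected chi-square. No control rate is given, so I assume 10% to 44%; the top is the risk that Protocol 2 gives for a cervix of 1 to 10 mm. The 90 itself cannot be rebuilt. A 40-point difference needs 15 to 24 per group, and a 40% relative reduction reaches 80% power at 90 only with a control rate near 51%. I therefore set the pessary rate, for each assumed control rate, at the value giving 80% power with 90 per arm.

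**3. Sensitivity, 99 per arm, 90 known and 9 unknown in each.** For x₁ and x₂ events with n per arm, d = x₁ − x₂ and S = x₁ + x₂, chi-square = 2n·d² / [S(2n − S)].

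Example, 20% control rate, 18 v 5 known events:
- Known births only (n = 90): 180 × 13² / (23 × 157) = 8.42, p = 0.004.
- Three unknown pessary women as events, 18 v 8 of 99: 198 × 10² / (26 × 172) = 4.43, p = 0.035.
- Four, 18 v 9: 198 × 9² / (27 × 171) = 3.47, p = 0.062.

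| Assumed control rate | Known events, control v pessary (of 90) | p, known births only | p, all unknown as non-events | Unknown pessary events (of 9) to reach p ≥ 0.05, unknown controls as non-events | Same, unknown controls at observed rate | p, all 9 pessary unknowns as events, controls as non-events |
|---|---|---|---|---|---|---|
| 10% | 9 v 1 | 0.009 | 0.009 | 2 | 3 | 0.81 |
| 15% | 14 v 3 | 0.005 | 0.005 | 3 | 4 | 0.67 |
| 20% | 18 v 5 | 0.004 | 0.004 | 4 | 6 | 0.44 |
| 25% | 22 v 8 | 0.005 | 0.005 | 4 | 6 | 0.37 |
| 30% | 27 v 12 | 0.007 | 0.007 | 4 | 7 | 0.32 |
| 40% | 36 v 19 | 0.006 | 0.007 | 5 | 8 | 0.22 |
| 44% | 40 v 22 | 0.005 | 0.006 | 5 | 9 | 0.18 |

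In the sixth column the nine unknown controls contribute 1, 1, 2, 2, 3, 4 and 4 events (9 × observed rate, rounded).

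**4. Direction.** With all nine unknown pessary women as events and unknown controls as non-events, the pessary count exceeds the control count only in the 10% row (1 + 9 = 10 v 9). In the next row it is 12 v 14, and the pessary count stays lower in every row after that.

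**5. Unequal loss, no true effect.** Suppose 10 of 99 are unknown in one arm and none in the other, all scored as non-events. The apparent rate in the first arm is p × 89/99. At true rates of 10, 20, 30 and 44% the spurious gap is p × 10/99 = 1.0, 2.0, 3.0 and 4.4 points. The chance of a significant result favouring that arm is about 4%, 6%, 7% and 9% (normal approximation) instead of 2.5%.

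**The case against.** Several points on the other side stand.

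- A reader might infer that an unknown birth is counted as a success. No passage says so; dropping or censoring fits the text equally well.
- A reader might take this to threaten the main result directly. SAP 6 makes Per Protocol the main analysis, and a woman whose delivery is unknown falls outside it. The unscored births sit in the ITT proportions and the Kaplan-Meier analysis.
- Many births should be known. Protocol 5.7 continues standard follow-up after withdrawal from the product, 5.8 names a records source, 5.4.5 closes each case at 36 6/7 weeks or at preterm birth, and section 8 asks for preterm births to be reported within 24 hours. The 10% is not a forecast of unknown births.
- Sections 5.5 to 5.7 concern withdrawn women. No passage says women lost to follow-up are kept; they remain only if they meet the SAP's ITT definition.
- The counts in step 3 require unknown pessary women to fare much worse than those observed: at a 20% control rate, 4 of 9 against 5 of 90.

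These points narrow the finding but do not close it. Sections 5.5 and 5.6 withdraw women from the study, not just from the product; SAP 9 does the same at pessary removal; and adverse events are recorded only to the last contact. No passage requires the birth of a woman who has left to be traced. Making Per Protocol the main analysis removes the scoring question there by leaving these women out, which is hard to square with the Protocol's intention-to-treat wording.

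**Conclusion.** The gap is real and follows from stated rules as well as from silence. Following the plan can leave deliveries unrecorded through arm-specific exits, and the ITT and Kaplan-Meier analyses have no rule for them.

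On assumed control rates of 10% to 44% and 9 unknown of 99 per arm, significance is lost when 2 to 5 of the unknown pessary women deliver preterm with unknown controls as non-events, or 3 to 9 with unknown controls at the observed rate. It would be tempting to say that a few women could reverse the finding. The figures show loss of significance; the direction changes only at the lowest rate with every unknown pessary woman an event. Equal loss scored as non-events leaves p almost unchanged, so the bias depends on loss, or risk among the lost, differing by arm. All event counts are assumptions.

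This should be corrected before the data are analysed.

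**What to change.** 1. **Collect the outcome.** In SAP 9 and 10, state that leaving treatment or the study does not end outcome collection. Obtain gestational age and cause of delivery for every randomized woman from the hospital file or treating physician (Protocol 5.8), subject to her consent. Reconcile early termination in SAP 9 with Protocol 5.5 to 5.7.
2. **State the scoring rule.** In the ITT comparison, a woman is a non-event only if documented undelivered at the cut-off or delivered before it for a non-spontaneous reason, never by default. In the Kaplan-Meier analysis, censor an unknown delivery at the last gestational age at which she was known to be undelivered.
3. **Show the sensitivity.** Report unknown deliveries by arm, and add a tipping-point table for the ITT comparison that varies the number of unknown women counted as events in each arm.

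Multiple imputation is optional; with few events per arm it may be unstable.

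The cost is some SAP wording, some record-tracing for women who leave, and one extra table.

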#### 5.7. Study participant withdrawal

The progesterone cerclage pessary will be removed if the patient requests so, or if there is any adverse event not responding to treatment alternatives such as pathological vaginal discharge non-responsive to antibiotic therapy. These participants will not be replaced and the information collected from them will be included in the analysis since this is based on the intention-to-treat principle.

Follow-up of subjects withdrawn from the investigational product will be the same as the standard follow-up.

## 5.8. Recording, quality control, and data management

Information about the characteristics of the participants, including demographics (race, age, parity, measures for calculation of body mass index [BMI]), and the medical and obstetrical records will be obtained directly from the participants and recorded in the study file. Information about the outcome of the pregnancy will be obtained from the hospital's medical records file or treating physician. Medical records of participants experiencing preterm birth labor before weeks 32 and 34 will be reviewed to determine the cause and establish whether the delivery was because of medical indication or spontaneous. Spontaneous deliveries will include those with prior preterm labor and those with rupture of membranes before the onset of labor. Quality control for screening, information management, and monitoring of adherence to protocol across the four sites will be performed regularly by the clinical study monitor.

## 6 MATERIALS AND SUPPLIES

Cerclage pessaries containing sustained-release progesterone will be manufactured by Laboratorios Andrómico S.A. Both the pessaries as well as the 200 mg progesterone soft capsules to be administered by vaginal route will be supplied to participants free of charge by Laboratorios Andrómico S.A.

- Vaginal formulations of the study:
  - Capsules containing 200 mg of micronized progesterone for vaginal administration.
  - Vaginal device consisting of a cerclage pessary containing 6.3 g of sustained-release progesterone.
  - Vaginal device consisting of a cerclage pessary containing 7.7 g of sustained-release progesterone.

Laboratorios Andrómico S.A. will be responsible for printing the applicable codes on every container of study formulation.

## 7 OUTCOMES OF INTEREST

### 7.1. Primary Outcomes:

Determination of the progesterone effective dose in the cerclage pessary by non-occurrence of spontaneous delivery before 32 and 34 weeks of gestation.

### 7.2. Secondary Outcomes:

#### 7.2.1. Occurrence of rupture of membranes:

7.2.1.1. Premature rupture of membranes before 32 and 34 weeks of gestation.

#### 7.2.2. Cervical anatomic changes

7.2.2.1. Cervical length before and after the insertion of the progesterone pessary.

7.2.2.2. Cervix position *relative to the longitudinal axis of the uterus* before and after insertion of the progesterone pessary considering that this measurement may be performed on the same day of the pessary insertion or at Visit 2.

7.2.2.3. Measurement of the utero-cervical angle formed by the posterior wall of the uterus and the longitudinal axis of the cervix before and after insertion of the progesterone pessary.

### 7.2.3 Acceptability

7.2.3.1 Ease of insertion. Measured by means of a questionnaire.

7.2.3.2. Pain of the patient at the time of insertion and during use of the pessary. The VAS will be applied from 1 to 10 at Visit 1 (admission, where questions 1 to 3 will be answered) and at the final study visit (where questions 4 and onwards will be answered).

7.2.3.3. Request for early removal of the pessary. Date, gestational age and reason for the pessary removal request will be recorded in the data record file.

7.2.3.4. Spontaneous expulsion of the pessary: Date and gestational age at the time of expulsion of the pessary without replacement will be recorded in the data record file.

7.2.3.5. Changes in vaginal discharge. The participant will be questioned about the presence, quantity, and physical characteristics of the discharge at every control visit. The clinical signs and symptoms of the patient will also be recorded.

### 7.2.4. Local safety

7.2.4.1. Pain, irritation, pruritus, infection occurring in the patient during treatment.

7.2.4.2. Major maternal complications attributable to the pessary such as chorioamnionitis, severe vaginal or cervical trauma.

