Secondary	
Occurrence of rupture of membranes: Premature rupture of membranes before 32 (31 6/7) and 34 (33 6/7) weeks of gestation.
 
Cervical anatomic changes
 
 
1. Cervical length and internal cervical os dilation before and after inserting the pessary.
 
2. Cervical position in relation to the uterus longitudinal axis before and after inserting the medicated pessary.
 
 
Acceptability:
 
 
1. Ease of insertion
 
2. Pain of the patient at the time of insertion
 
3. Assessment based on the VAS during use
 
4. Spontaneous expulsion of the pessary
 
5. Request for early removal of the pessary
 
6. Subjective changes of vaginal discharge
 
 
Local safety: Major maternal complications attributable to the pessary (chorioamnionitis, severe vaginal or cervical trauma).

Length of the Study	21 – 48 months

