## 8 ADVERSE EVENTS

An adverse experience is defined as an unfavorable and unexpected change in the structure, function, or chemistry of the body, transiently associated with the use of the study product, whether or not related to the use of the drug. Any worsening (i.e., any adverse change clinically significant in terms of frequency or severity) of a pre-existing condition that is transiently associated with use of the study product is also an adverse experience.

Adverse events will be documented from the time of enrollment (i.e., at the time of signing the informed consent form) through the last scheduled contact as per the protocol, i.e., the date of the last visit/contact (may be a phone call, for example, in case the participant withdraws from the study).

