#### **Definition of Adverse Event of Special Interest**

Adverse events of special interest are adverse events considered important for assessment of the safety profile regardless of seriousness, expectancy, and severity classification.

Preterm birth is the birth of a fetus before 37 weeks of pregnancy. Preterm birth will be considered an event of special interest and should consequently be reported within 24 hours.

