### 9.2. Statistical analysis

For quantitative variables, descriptive statistics will be used (mean, standard deviation, minimum, median, maximum, 95% CI, and number of observations), whereas for categorical variables, frequencies and percentages analyses will be carried out. Results will be tabulated by treatment arm and pooled. The different vaginal formulations and progesterone will be formally compared. Results on efficacy and safety will be studied for each group separately and pooled, if relevant.

The proportion of women reporting adverse events during treatment will be cross-compared between the different doses using the Fisher's exact test or the Chi-square test.

All statistical analyses will be performed using the statistical software SPSS (Version 12) or Epistat 4.0.

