11. SAFETY ANALYSIS

11.1 ADVERSE EVENTS

The evaluation of adverse events (AE) will be monitored throughout the study, by direct observation at each visit.

All AE will be recorded (according to the definition), and not only those where the investigator suspects a causal relationship with the treatment. Adverse events of interest; i.e., those in which the investigator at each site must pay particular attention are those that have been defined as local safety (pain, irritation, itching and infection) and major maternal complications attributable to the pessary as chorioamnionitis, severe vaginal or cervical trauma.

All the AE will be encoded in MedDRA version 19.1 or higher to be summarized by System Organ Class (SOC) / Preferred Term (PT).

The following 3 overview tables will be generated by treatment group and overall:

1) Summary of the number and percentage of subjects with at least 1:

- AE
- Serious AE
- Non-serious AE
- Unexpected AE
- Severe AE
- Related AE
- Related serious AE
- AE leading to discontinuation from IMP

The percentage denominator will be the number of subjects in the safety analysis.

2) Summary presenting the number of AEs per subject categorized as 0, 1, 2, 3, 4, 5, and >5;

3) Summary of the number and percentage of AEs for:

- AEs
- Serious AEs
- Non-serious AEs
- Unexpected AEs
- Related AEs
- Related serious AEs
- AEs leading to discontinuation from IMP

The percentage denominator will be the total number of AEs.

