11.2 INCIDENCE RATES AND NUMBER OF EVENTS

The incidence of an AE is defined as the number of subjects with occurrence of this AE during the period of interest. The incidence rate (CIR for crude incidence rate) of an AE is defined as the number of subjects with occurrence of this AE during the period of interest divided by the total number of subjects in the respective group (e.g., dose group).

The incidence, incidence rate, the number of events and the percentage of events (related to the total number of events) will be summarized by PT (sorted by decreasing incidence rate in the overall column) for

- AEs
- related AEs
- AEs leading to treatment discontinuation

A separate table per type of AE will be prepared. Only AEs occurring in at least 5% of subjects overall will be included in the text. Tables will be sorted by decreasing incidence overall.

The incidence, incidence rate, the number of events and the percentage of events (related to the total number of events) will be summarized by SOC and PT (sorted alphabetically) for each

- AEs
- serious AEs
- non-serious AEs
- related AEs
- serious treatment related AEs
- AEs leading to treatment discontinuation

For serious AEs, the incidence, incidence rate, the number of events, and the percentage of events will also be presented for serious treatment related AEs, serious fatal AEs and serious fatal related AEs.

For all enrolled subjects, the incidence, incidence rate, the number of events, and the percentage of events (related to the total number of events) will be summarized by SOC and PT (sorted alphabetically) for each.

The number and percentage of events will be summarized by SOC and PT (sorted alphabetically) for the following AE descriptors. Presentation will be for AEs only.

- intensity: mild, moderate, severe
- causal relationship to the imp: related (with subcategories: possible, probable/likely, certain), not related (with subcategories: not related, unlikely), unknown (with subcategories: conditional/unclassified, unassessable/unclassifiable, causal relationship missing)
- outcome: recovered/resolved, recovering/resolving, not recovered/not resolved, recovered/resolved with sequelae, fatal, unknown
- non-IMP related countermeasures: none, newly started medication, others
- action taken with imp: dose not changed, dose reduced, drug interrupted, trial discontinuation, unknown.

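### The major maternal complications outcome is defined by attribution to the pessary, so it has no capsule-arm rate, and the SAP plans no grouped by-arm comparison for it

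*Protocol*

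**What the plan says.** Protocol 7.2.4 has two local-safety items. The first covers pain, irritation, pruritus and infection arising during treatment, with no causal condition. The second is "Major maternal complications attributable to the pessary such as chorioamnionitis, severe vaginal or cervical trauma". The synopsis has the same condition, and SAP 11.1 repeats it when it lists adverse events of interest: "major maternal complications attributable to the pessary as chorioamnionitis, severe vaginal or cervical trauma".

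Recording of adverse events is wider than this outcome. The protocol's definition in section 8 applies "whether or not related to the use of the drug", and SAP 11.1 states: "All AE will be recorded (according to the definition), and not only those where the investigator suspects a causal relationship with the treatment".

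On reporting, SAP 11.1 plans three overview tables by treatment group and overall. SAP 11.2 defines incidence with the group size as denominator and lists tables by preferred term (PT) and by system organ class (SOC) and PT, including tables for serious events. For the report text it adds: "Only AEs occurring in at least 5% of subjects overall will be included in the text".

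On testing, protocol 9.2 says that the proportion of women with adverse events will be "cross-compared between the different doses using the Fisher's exact test or the Chi-square test". SAP section 11 names no between-arm test.

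**The concern.** This is a randomized trial with a concurrent control, so the natural safety question is whether chorioamnionitis or trauma is more frequent with a pessary than with capsules. An outcome that requires attribution to the pessary cannot answer it. The control value is fixed at zero before any data are collected. In the pessary arms, a case counts only if an investigator who knows the assignment judges the device responsible. Chorioamnionitis does not need a pessary in order to occur, so the attributed count measures opinion as well as risk, and the error could go in either direction.

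The SAP does not repair this. It names the events as ones of interest and then plans no output for them as a group. A comparison would have to be put together afterwards from separate preferred terms, by people who may already have seen the results. An excess in one dose group could also be left out of the report text because the cut-off averages over all three arms.

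**Working it through.** The documents state no figure for these complications, so there is none to reproduce. The check has three parts.

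**1. What is and is not specified**

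| Element | Named complications | Comparator in the same documents |
|---|---|---|
| Causal condition | Yes (synopsis, protocol 7.2.4, SAP 11.1) | None for pain, irritation, pruritus, infection (protocol 7.2.4) |
| Overview row or term grouping | None in SAP 11.1 or 11.2 | Serious, severe, related and unexpected AEs have rows |
| Between-arm test in the SAP | None | Membrane rupture, also identified from AE records, gets a CMH test (SAP section 10) |
| Individual terms by group | Yes, SOC/PT and serious-AE tables, no cut-off stated | Same |

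**2. The 5% in-text rule as a count**

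Inputs: 90 per arm, 270 in total (protocol 4.1); 99 per arm, 297 in total, with the dropout allowance (protocol 9.1). The SAP runs safety on its ITT set, which requires at least one visit after the first, so the real denominator may differ.

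- N = 270: 0.05 × 270 = 13.5, so 14 women are needed and 13 fall below.
- N = 297: 0.05 × 297 = 14.85, so 15 are needed and 14 fall below.

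Two-sided Fisher tests for splits that stay below the cut-off:

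| Pessary | Capsule | Rates | p |
|---|---|---|---|
| 13/90 (one arm) | 0/90 | 14.4% v 0% | 0.0002 |
| 13/180 (both arms) | 0/90 | 7.2% v 0% | 0.006 |
| 12/180 (both arms) | 1/90 | 6.7% v 1.1% | 0.066 |
| 14/99 (one arm) | 0/99 | 14.1% v 0% | 0.00007 |
| 14/198 (both arms) | 0/99 | 7.1% v 0% | 0.006 |

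For the first row, with equal arms, p = 2 × C(90,13)/C(180,13) = 0.00015. The smallest counts that reach p<0.05 against 0/90 are 6/90 in one arm (p=0.029) and 9/180 over both arms (p=0.032). The rule is applied term by term, so a complication coded under several terms falls below it more easily. These are boundary cases, not predictions.

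**3. What a test could detect**

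The documents give no expected rates. The pairs below are assumptions. Power is for Fisher's exact test at two-sided 0.05; the last column is the sample size from the uncorrected two-proportion formula.

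| Capsule v pessary (assumed) | 90 v 90 | 90 v 180 | Per arm for 80% |
|---|---|---|---|
| 1% v 5% | 15% | 27% | 285 |
| 2% v 6% | 14% | 23% | 376 |
| 2% v 8% | 32% | 48% | 206 |
| 2% v 10% | 52% | 70% | 138 |

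At 2% v 6% in both pessary arms, the expected overall rate is (2 + 6 + 6)/3 = 4.7%. Even a threefold rate would then be expected to fall just under the in-text cut-off. With 0/90 events, the exact two-sided 95% upper limit is 1 − 0.025^(1/90) = 4.0%. An interval is therefore more informative than a test.

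**The case against.** The strongest reply is that the comparison remains possible. Every adverse event is recorded regardless of cause, incidence is per group, and the SOC/PT and serious-AE tables have no stated cut-off. Under the protocol's definition, any admission or clinically significant event is serious, so chorioamnionitis or severe trauma would very likely appear in the serious-AE tables. This stands. A reader might infer that these complications go uncounted on capsules or cannot be compared at all. The documents do not support that: the restriction is on the defined outcome, not on AE recording.

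The 5% rule likewise governs what appears in the text. The splits above show worst-case placement in the report, not lost data.

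A reader might also infer that the SAP dropped a planned capsule-against-pessary test. Protocol 9.2 speaks of comparison between doses and of adverse events in general, so it is unclear whether capsules are included. The SAP also makes the protocol the final reference, so its silence does not clearly cancel the test.

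Finally, the protocol's event of special interest is preterm birth, which is not on the SAP's list. Little follows from that. The protocol entry sets a reporting duty ("Preterm birth will be considered an event of special interest and should consequently be reported within 24 hours"), and spontaneous preterm birth is already compared between arms for efficacy.

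It is also fair to say that the study is exploratory and safety is a secondary objective. That lowers the stakes, but it does not give the defined outcome a control rate.

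**Conclusion.** The point holds in a limited form. As defined in three places, the major maternal complications outcome is non-comparative: zero on capsules by construction, and dependent on open-label attribution on pessaries. SAP section 11 adds no row, grouping or between-arm comparison. This follows from the wording alone and needs no assumption.

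The effect of the 5% rule is secondary. Up to 13 of 270 women (14 of 297) with a given term can stay out of the report text, even if all are in one arm. That figure assumes the planned denominators and an extreme split.

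Power is low across most of the assumed rates, so the gap is one of estimation and not of a missing significance test.

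**What to change.** - In protocol 7.2.4, the synopsis and SAP 11.1, define the outcome as chorioamnionitis, severe cervical trauma and severe vaginal trauma from any cause, counted in all three arms. Keep investigator attribution as a separate descriptive column.
- In the SAP, list the preferred terms that make up each event, and say how severe trauma is identified from the recorded data.
- Add one table by arm giving women with each event, with the risk difference and exact 95% confidence interval for each pessary arm against capsules. Label any Fisher test as supportive.
- Exempt these events from the 5% in-text rule.
- State whether the protocol 9.2 comparison of women with adverse events is kept, and whether it includes the capsule arm.

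The cost is one table and wording changes in both documents. No new data are needed, because the events are already recorded regardless of cause. If the sponsor regards the protocol wording as a substantial amendment, protocol section 12 requires ethics committee approval first.
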